#### Improved Future Implementation

At the completion of the 6-month cycling intervention and again following the 3-month maintenance period, all participants will complete an interview with the study team during the last cycling session. This interview is designed to inform the research team about the effectiveness and delivery of the intervention from the participant's perspective. The questionnaire has been developed from the Center for Disease Control's Evaluation Framework. The following questions will be asked:

1. Why did you join this program? (posttest only)
2. As you became involved, did you discover other reasons for participating that you did not initially anticipate? (posttest only)
3. In what way(s) has the program met your expectations and/or needs?
4. In what way(s) has the program failed to meet your expectations and/or needs?
5. In your opinion, what are the most important outcomes or benefits that have resulted from your participation? (posttest only)
6. How would you rate the overall success of (the in-home cycling program or follow-up period) using a scale from one to ten, where one is a complete failure and ten is a total success? Why?
7. Are there other factors or circumstances that you think contributed to the success (or failure) of the program? Please explain.
8. Did you experience any challenges or barriers (e.g., competing priorities, organizational challenges, job role changes, technological challenges) that kept you from participating in the program at the level that you would have liked to participate?
  - a. Were you able to participate in as many sessions as you wanted to participate in? If not, why?
9. Can you think of anything the team could do differently to address the challenges or barriers that might keep people from participating fully?

### **Posttest assessment**

All measures listed in the Pre-test assessment protocol will be included at posttest except those measures listed under “Intake and review of forms” and “Screening measures”

### **3-month follow-up assessment**

All measures listed in the Pre-test assessment protocol will be included at 3-month follow-up except those measures listed under “Intake and review of forms” and “Screening measures”

During all testing sessions:

1. **Rest breaks** – Participants will be frequently prompted and given rest breaks regularly and as needed.
2. **Adherence to medication schedules** – As medication management can significantly impact the safety of the individual as well as the outcomes of the data collection sessions, individuals will be instructed to maintain their medication schedules during testing procedures.
3. **Safety protocol during testing** - To minimize risks to participants during evaluation sessions, a spotter to assist in preventing falls will be present as needed and a gait belt can be donned as necessary. Testing staff will also be prepared to provide first aid for minor injuries and to contact emergency healthcare personnel in the event of a more serious injury. In the event of a more serious, life-threatening emergency, the emergency protocol described below will be implemented.

## Study 2 Intervention

Qualifying participants will be stratified by age and motor symptom severity as assessed by the UPDRS (UPDRS Motor score (+/- 4 points) and then randomly assigned to either the social or solo in-home cycling group.

The initial cycling session for both groups will occur in the participant's home with two members of the testing team. The team will set up the bike and properly fit it to the individual rider. Additionally, the team will ensure the stationary bike is safe, secure and in an area free of clutter and dangerous obstacles. Study team members will set-up and establish a secure connection using the MiFi device, if necessary, at this time. Both groups will be provided with a MiFi wireless internet connection if needed to allow for data collection of cycling and activity monitor data.

For those in the social cycling group, a tablet will be installed and mounted to the recumbent bike. A remote connection will be made to an individual at the UW to test the Skype connection and show the participant how to use the technology. This testing will lessen the likelihood of study dropout due to frustration with the technology component. An additional failsafe has been built into the computer system which allows us to remotely control the software and assist the participant if necessary. For privacy, we will not be able to access the machine without the participant clicking the allow button on the screen.

The selected recumbent bike has been chosen based on a number of factors which make it safe, user friendly and allow for the tracking of the desired speed and duration data. The bike weighs over 100 pounds and has a wide footprint to prevent tipping as well as a low ground clearance step through to allow individuals with PD to get on and off the bike without falling. The saddle is a wide padded seat with a fully supportive backrest to promote comfort but also maximize rider safety. Pulse sensors are located on the display mount and seat handles and pulse readings are incorporated into the software which allows for real-time tracking of the speed and resistance settings of the cycle. Additionally, this bike comes with a large digital display and preprogrammed cycling sessions that will allow a programmed and progressive exercise plan to be implemented after the 6-month group cycling program ends.

Scheduled training sessions will occur in the individual's home with digital display connecting the individual with PD to a member of the research team. Training sessions will occur three times per week for 6 months. Each training session will consist of up to 30 minutes of cycling at a target speed with a 2-minute warm-up session, and a 2-minute cool down at the end of the session. Actual intervention times will be based on the individual's endurance level and will increase over the sessions.

When beginning the cycling sessions, participants will have their maximum and target heart rate calculated. The calculation for target heart rate is  $220 - \text{participant age}$ . Target heart rate will be calculated using a span of 50-85% of the calculated maximum (50 to 70% of maximum = moderate and 70 to 85% of maximum = vigorous exercise). Individuals will be provided with a printout of these calculations as well as the weekly exercise goals established by the Centers for Disease Control and Prevention and the American Heart Association (see Appendix I and II). Participants will not be instructed to cycle on the days without scheduled cycling sessions, but they will be informed of the CDC and American Heart Association recommendations and told that they are invited to use the bike outside of the scheduled sessions. All participants will be asked to complete a daily exercise log (Appendix III). Logbooks entries will be collected from all participants at four-week intervals and reviewed by the study team. During the first testing session of each week a study team member will complete a falls assessment with each individual.

Participants will be provided with an information sheet to describe the cycling sessions, their target heart rate, perceived exertion and the exercise journal (appendix V, "In-Home Cycling Program – Partnered Cycling -") and the one page "How much physical activity do you need" document from the American Heart Association. For those in the partnered cycling group, we will gradually increase the duration of the cycling sessions for the first 12 weeks while verbally coaching them to keep their heart rate between 50 and 70% of their calculated maximum. The sessions during the first week will last 5 minutes. As the individual exercises, it will take a greater speed to attain the desired heart rate. For the second twelve weeks, the research assistant will help the participants to monitor the average speed of the final session of the previous week and suggest an increase in the target speed to increase the individual's heart rate. The research assistant will also assist the individual in monitoring their heart rate to stay in the upper end of the target intensity range. The goal durations and intensities for each week are listed in table 1.

Week	Target Duration	Target Intensity
------	-----------------	------------------

1	5 mins	50 – 70% of max heart rate
2	10 mins	50 – 70% of max heart rate
3	12 mins	50 – 70% of max heart rate
4	15 mins	50 – 70% of max heart rate
5	17 mins	50 – 70% of max heart rate
6	20 mins	50 – 70% of max heart rate
7	20 mins	50 – 70% of max heart rate
8	22 mins	50 – 70% of max heart rate
9	25 mins	50 – 70% of max heart rate
10	25 mins	60 – 70% of max heart rate
11	30 mins	50 – 70% of max heart rate
12	30 mins	60 – 70% of max heart rate
13	30 mins	60 – 70% of max heart rate
14	30 mins	60 – 70% of max heart rate
15	30 mins	60 – 70% of max heart rate
16	30 mins	60 – 70% of max heart rate
17	30 mins	60 – 70% of max heart rate
18	30 mins	60 – 70% of max heart rate
19	30 mins	60 – 70% of max heart rate
20	30 mins	60 – 70% of max heart rate
21	30 mins	60 – 70% of max heart rate
22	30 mins	60 – 70% of max heart rate
23	30 mins	60 – 70% of max heart rate
24	30 mins	60 – 70% of max heart rate

For those assigned to the solo cycling group, three sessions will be scheduled during the first week of the program. A study team member will call the individual 10 minutes after the scheduled completion time during the first week to see if the individual needs any extra assistance with the bike or the journal. Each individual will be provided an information sheet to describe the cycling sessions, their target heart rate, perceived exertion and the exercise journal (appendix VI, “In-Home Cycling Program – Independent Cycling –”) and the one page “How much physical activity do you need” document from the American Heart Association. Sessions will be self-directed by the participant; however, a suggested progression is provided on page 4 of the “In-Home Cycling Program” document. All individuals in the solo group will be asked to complete the daily exercise journal. At the end of each week, a study team member will contact the individuals in the solo cycling group via a telephone call to ask about falls and provide the individual with their average speed of the final session of the previous week.

All participants will be asked to not begin any new exercise programs once enrolled in the study, but will not be asked to discontinue any current physical activity. Information about current physical activity level will be collected at all time points including the exercise journal.

Activity monitors (Garmin VívoSmart 3) will be donned by all study participants throughout the duration of the study starting at the time of either pre-test or baseline assessment depending on group assignment and continuing through the 3-month follow-up. These devices allow for activity monitoring as well as online monitoring of heartrate. Participants will be asked to wear the activity monitors at all times once enrolled in the study. Number of steps taken daily and amount of aerobic activity will be used to compare changes in activity level. During the exercise sessions, heartrate will be monitored via the heartrate monitor on the bike and the heartrate monitor on the activity monitors.

At the time of enrollment, all participants will have their maximum and target heartrate calculated. The calculation for target heartrate is  $220 - \text{participant age}$ . Target heartrate will be calculated using a span of 50-85% of the calculated maximum (50 to 70% of maximum = moderate and 70 to 85% of maximum = vigorous exercise). Individuals will be provided with a printout of these calculations as well as the weekly exercise goals

established by the Centers for Disease Control and Prevention and the American Heart Association (see Appendix I and II).

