### **Study 2**

Examine the effects of social engagement during in-home exercise on a small sample of individuals with Parkinson Disease (PD). This pilot investigation will directly measure the effect of social support and engagement for rural dwelling individuals with PD.

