### **Study 2**

**SPECIFIC AIM 1:** Determine whether incorporation of social interaction during physical activity significantly improves task adherence and increases task stamina as compared to solo cycling.

**Hypothesis 1a:** Those individuals participating in socially engaged cycling will complete a significantly greater number of cycling sessions than individuals in the solo cycling group.

**Hypothesis 1b:** Individuals in the social cycling group will cycle for longer durations at each session than solo cyclists, despite the long term goal being 30 minutes per session for both groups.

**SPECIFIC AIM 2:** Determine whether incorporation of social interaction during physical activity significantly improves activities of daily living, fall rate and quantity of movement for individuals with PD. The primary variables for this aim are Performance Assessment of Self-care Skills Assessment scores, gait velocity and step count.

**Hypothesis 2a:** Socially engaged exercise will result in significantly greater improvement in measures of instrumented activities of daily living (IADL; as measured by the Performance Assessment of Self-care Skills (PASS) assessment) as compared to solo cycling.

**Hypothesis 2b:** Fall rate will be non-significantly improved with socially engaged cycling but not with solo cycling. Weekly calls will be placed to both groups to record fall rate. Falls data will allow for effect size calculations for future applications.

**Hypothesis 2c:** Overall activity level, as measured by an activity monitor, will increase with socially engaged cycling but not with solo cycling.

**Study Duration:** This study will be conducted over the next 4 years including all data analysis, manuscript and grant proposal submissions.

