Study 2: 12 people with PD, living in rural settings or with barriers to travel and who have reported that proximity to community-based exercise is a primary barrier to enrollment will be enrolled in the study. Qualified individuals will be paired based on disease severity (score on subsection III of the UPDRS) and age and randomly assigned to either the social cycling group or solo cycling group for 6 months. Both groups will have an exercise bike delivered to their home, custom fit to their needs and installed in a safe location. Sessions will consist of up to 30 minutes of cycling. Those in the social group will cycling while engaged in social interaction with a research staff member, thus providing a social/community aspect that would not otherwise be present. Those in the solo group will have a target duration and intensity but will exercise without a partner.

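### Study 2 compares a staff-accompanied, coached video package with self-directed cycling, so a difference cannot be credited to social engagement alone

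*Combined protocol and SAP*

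**What the plan says.** The Project Summary says of Study 2: "This pilot investigation will directly measure the effect of social support and engagement for rural dwelling individuals with PD". The same claim stands in the Layperson summary, under Substudies, and in section 1 of the Data and Safety Monitoring Plan (Appendix IV).

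Under Specific Aims, Study 2, Aim 1 reads: "Determine whether incorporation of social interaction during physical activity significantly improves task adherence and increases task stamina as compared to solo cycling". Hypothesis 1a expects social cyclists to "complete a significantly greater number of cycling sessions than individuals in the solo cycling group". Hypothesis 1b expects them to ride longer per session, although the long-term goal of 30 minutes is common to both groups. Aim 2 attributes differences in daily living skills, falls and movement to social interaction in the same way.

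Research Design presents the contrast as partner versus no partner: "Those in the solo group will have a target duration and intensity but will exercise without a partner".

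Study 2 Intervention describes delivery. In the partnered group, staff lengthen sessions over the first 12 weeks while "verbally coaching them to keep their heart rate between 50 and 70% of their calculated maximum". In the second 12 weeks they suggest higher target speeds. For the solo group, "three sessions will be scheduled during the first week of the program", with a support call after the scheduled finishing time. The text then says: "Sessions will be self-directed by the participant; however, a suggested progression is provided on page 4" (of the participant's information document). A weekly call asks about falls and reports average speed.

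Power and Statistical Analysis plans a 2 x 2 repeated measures ANOVA, with time and intervention as factors, for both studies.

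**The concern.** Aim 1 and the statement of purpose name one ingredient, social interaction, as what is being tested. The assigned treatments differ in several, and at least three of the others can act directly on the Aim 1 outcomes.

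- A standing appointment with a staff member can raise the number of sessions completed.
- Staff who lengthen sessions week by week can raise minutes per session.
- Live prompting on heart rate and speed can raise exercise dose, and through dose the Aim 2 outcomes (PASS, gait velocity, step count).

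None of these needs a social effect. Randomisation and pairing on severity and age do not help, because the extra components belong to the assigned arm and are not baseline imbalances.

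The distinction matters for the plan's own question. Background and Significance calls the social benefit hard to separate out, names one-to-one staffing as a scalability problem, and says it is unknown whether face-to-face contact helps people with PD. Research Design seeks the best delivery method. A reader told that social engagement improved adherence would draw a different lesson from one told that booked, coached video sessions did.

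**Working it through.** The plan gives no figure on this point to reproduce. The check sets the arms side by side, counts scheduled contact, and asks what the planned contrast can identify.

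**1. Components by arm** (Study 2 Intervention, and the section on minimising risks during exercise)

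| Component | Social | Solo |
|---|---|---|
| Bike, activity monitor, exercise log | yes | yes |
| Heart-rate targets, moderate-level instruction | yes | yes |
| Sessions booked | three a week for 6 months, with staff link | three, in week 1 |
| Tablet and video link | yes | not described |
| Heart rate and exertion in session | staff monitor heart rate continuously and ask about exertion every 5 minutes | participant uses reference card |
| Heart-rate coaching | verbal, live | none described |
| Duration, weeks 1-12 | raised by staff | written suggestion, self-directed |
| Speed, weeks 13-24 | staff suggest an increase | average speed reported by telephone; no suggested increase described |
| Company during the ride | yes | no |

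Only the last row is the named ingredient. The rows on booking, monitoring, coaching, duration and speed also differ.

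**2. Scheduled contact**

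- Social sessions: 3 per week x 24 weeks = 72. Solo booked sessions: 3. Difference: 72 - 3 = 69.
- Social target riding time, from the weekly table: weeks 1-10 sum to 5 + 10 + 12 + 15 + 17 + 20 + 20 + 22 + 25 + 25 = 171 minutes. Weeks 11-24 add 14 x 30 = 420. The total is 591 minutes per weekly slot, and 591 x 3 = 1,773 minutes, about 29.6 hours.
- Solo calls: 3 in week 1 (one per scheduled session) + 24 weekly = 27, none during a ride. Call length is not given. Assuming 5 to 15 minutes each, contact is 27 x 5 / 60 = 2.25 hours to 27 x 15 / 60 = 6.75 hours.
- Ratio of staff contact time: 29.55 / 6.75 = 4.4 to 29.55 / 2.25 = 13.1.

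**3. What the contrast identifies**

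Let S be the effect of company and C the combined effect of booking, monitoring, coaching and staff-driven progression. Taking the effects as additive for simplicity, the expected difference between arms is D = S + C. Every social participant is assigned both and no solo participant is assigned either beyond the shared elements, so the data give one equation in two unknowns. A time-by-intervention term estimates D. No factor in the planned ANOVA, and no other planned analysis, varies S while holding C fixed.

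For Hypothesis 1b the problem is sharpest: session duration is something staff actively increase in one arm, so the outcome is partly the treatment.

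**The case against.** The strongest reply is that a comparison of packages is legitimate in a 12-person pilot. Background and Significance describes the contrast as solo versus partnered and treats monitoring and intensity feedback as part of face-to-face interaction. That stands as a defence of the design. It does not defend the statement that the effect of social support is measured directly.

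The solo arm is also not without structure. It has heart-rate targets, the common moderate-level instruction, first-week support calls, a written progression and a weekly report of average speed. The social arm uses that same speed measure when raising targets in weeks 13-24. This narrows the gap, but live delivery still differs.

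The count of 72 depends on reading the general session description as the social arm's, since it carries no arm label. Its staff video link, the tablet supplied to the social group only, and the separate solo description support that reading.

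A reader might infer more than the documents support:

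- *That Research Design and Study 2 Intervention contradict each other on solo targets.* Self-directed riding is compatible with having targets, and the solo arm is given them.
- *That the written weekly targets differ between arms.* The solo progression page is not in the available text, so this cannot be checked.
- *That sessions and minutes are the study's main outcomes.* They are the Aim 1 outcomes. Aim 2 names PASS, gait velocity and step count as its primary variables.
- *That the next trial would be built on the wrong ingredient.* The power section ties effect size estimation for the subsequent proposal to the 40-person Study 1.

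**Conclusion.** The point holds as a mismatch between claim and contrast. A between-arm difference in Study 2 would show the effect of staff-accompanied, coached video sessions against self-directed cycling. It would not show the effect of social engagement alone. The attribution is weakest for sessions completed and session duration.

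The size is a difference in delivery: about 72 staff-connected sessions against 3 booked ones, and roughly 4 to 13 times the staff contact time if calls last 5 to 15 minutes. The first figure assumes the general session description applies to the social arm. The second also assumes sessions run at the tabled targets, without warm-up or cool-down, and one support call per week-1 session.

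Neither figure says how much of an observed difference would be social. That share is not identified, and the documents support no number for it.

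**What to change.** In the Layperson summary, Project Summary, Specific Aims (Study 2), Substudies, and section 1 of Appendix IV, describe the Study 2 contrast as *staff-accompanied, coached video cycling sessions versus self-directed solo cycling*. Carry the same wording into both aims, the hypotheses and the eventual conclusion, and remove the statement that the pilot directly measures the effect of social support and engagement. All the listed places need the change, because the claim is repeated in each.

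This changes no procedure. Its cost is a narrower claim.

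As an option, session booking could be aligned between arms through the weekly call the solo group already receives. That would reduce the confounding. It would leave live monitoring, coaching and staff-driven progression different, so it would not justify keeping the social-only claim. Its staffing cost cannot be judged, because call length and staffing are not given.

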**Maximum heartrate: 140 beats/minute**

**Target heartrate: moderate = 70 to 98 beats/min**  
**vigorous = 98 to 119 beats/min**

Weekly goal: 150 minutes of moderate exercise  
or  
75 minutes of vigorous exercise

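### The target heart rate printed for riders extends to 85% of maximum, while Table 1 and the moderate-only safety instruction stop at 70%

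*Combined protocol and SAP*

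**What the plan says.** **Definition of the target.** The Study 1 Intervention section (Cycling) and two places in the Study 2 Intervention section carry the same definition. It opens with "The calculation for target heartrate is", followed by 220 minus the participant's age. It continues: "Target heartrate will be calculated using a span of 50-85% of the calculated maximum" (the other Study 2 place spells it "Target heart rate will be calculated using a span of 50-85% of the calculated maximum"). The span is divided in brackets: "50 to 70% of maximum = moderate and 70 to 85% of maximum = vigorous exercise".

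**What the rider receives.** Each person gets a printout of these values with the CDC and American Heart Association weekly goals. Appendix I shows it for an 80-year-old: "Maximum heartrate: 140 beats/minute", then "Target heartrate: moderate = 70 to 98 beats/min", then "vigorous = 98 to 119 beats/min". The weekly goal offers 150 moderate minutes or "75 minutes of vigorous exercise". The section on minimizing risks during exercise, repeated in Appendix IV section 3.7, has each rider's calculated maximum and target posted on the bike.

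**Intended dose.** Table 1, printed in both Intervention sections, gives 50–70% of maximum in weeks 1 to 9 and week 11, and 60–70% in week 10 and weeks 12 to 24. As part of the protection against cardiovascular events, the risk section and Appendix IV section 3.7 tell participants in every group to aim for moderate exertion.

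**The concern.** One term, target heart rate, has two upper limits. The definition and the printout put it at 85% of maximum. The weekly schedule and the safety instruction put it at 70%. Nothing in the available text says that the vigorous zone is for reference only. The definition also attaches the word target to the formula for the maximum.

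What is at stake is agreement between the number in front of the rider and the dose that the protocol intends. This matters most where nobody is coaching:

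- the Study 2 solo arm, whose sessions are self-directed;
- the extra rides that participants are invited to take;
- the three-month maintenance phase of Study 1.

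Entrants are people who exercise for less than 20 minutes a week. The heart-rate trigger for ending a session, in the Follow-up Protocol, is a large and prolonged excess over the maximum, so it does not hold riders to 70%.

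**Working it through.** **Inputs**
- Maximum = 220 − age (Intervention sections; confirmed by the Appendix I example).
- Stated target span: 50% to 85% of maximum, with moderate ending at 70% (Intervention sections).
- Intended ceiling: 70% of maximum (Table 1, all 24 weeks; moderate instruction, all groups).
- Minimum age 45 (inclusion criteria); age 80 (Appendix I). Ages 60 and 70 are illustrative.

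**Step 1: reproduce Appendix I.** At age 80, maximum = 220 − 80 = 140.
- 0.50 × 140 = 70
- 0.70 × 140 = 98
- 0.85 × 140 = 119

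These match the printed 140, 70 to 98 and 98 to 119 exactly. So 220 minus age is the maximum, and calling it the target in the Intervention sections is a labelling error.

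**Step 2: distance between the two ceilings.** Gap = (0.85 − 0.70) × maximum = 0.15 × maximum.

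| Age | Maximum | 50% | 70% | 85% | Gap (beats/min) |
|---|---|---|---|---|---|
| 45 | 175 | 87.5 | 122.5 | 148.75 | 26.25 |
| 60 | 160 | 80 | 112 | 136 | 24 |
| 70 | 150 | 75 | 105 | 127.5 | 22.5 |
| 80 | 140 | 70 | 98 | 119 | 21 |

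**Step 3: does the text choose between them?** It does so in part. The moderate instruction identifies the zone to ride in, and the printout labels that zone. But the definition and the printout still present both zones as target, and no sentence limits the second to background information.

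**Step 4: after correction.** With the target held to the moderate zone, the age-80 printout would show 70 to 98 as the study target. In the weeks when Table 1 asks for 60–70%, the range would be 84 to 98, since 0.60 × 140 = 84.

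**The case against.** The strongest reply is that two labelled zones, plus an instruction to use one of them, do not amount to a contradiction. The printout puts the moderate range on its own line, and the risk section sends everyone to it. The vigorous line also has a plausible purpose: without it a rider could not interpret the alternative weekly goal. Participants are informed of those goals and invited to ride more; they are not told to ride hard. Other safeguards reach uncoached riders:

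- Appendix I warns against overexertion.
- The perceived-exertion scale is on the bike display, with moderate set at 3 to 5.
- Exercise logs record perceived exertion and highest heart rate, and are reviewed every four weeks.
- In Study 1 maintenance, staff set up each person's programme on the bike.

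The risk section also says that the information sheets (Appendices V and VI) highlight target ranges. All of this stands, and it lowers the weight of the point. It does not remove the mismatch, because both zones remain under the target heading.

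Four stronger readings are tempting but not supported:

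- **Staff will coach partnered riders towards 85% in weeks 13 to 24.** The text does speak of the upper end of the target range, but the next sentence refers to Table 1, which gives 60–70%.
- **The gap measures exposure or harm, or separates the arms.** It is a distance between two printed limits. Likewise, the share of the span above 70%, and the fraction of maintenance rides that a health coach attends, say nothing about how hard anyone rode. Both Study 2 arms receive the same definition.
- **Weeks 10 to 12 of Table 1 are another error.** The intensity floor drops in week 11 just as duration rises from 25 to 30 minutes, and returns in week 12. That can be deliberate.
- **HRR points to a second, competing heart-rate method.** It is an undefined abbreviation, tied by its sentence to what was described before.

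**Conclusion.** The inconsistency is real and is in the current text. The stated target exceeds the protocol's own intensity ceiling by 15% of maximum at every age, from 26.25 beats/min at age 45 to 21 at age 80, and the formula for the maximum is labelled as the target.

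The likely consequence is small and confined mainly to uncoached riding. Sample size and the planned analysis are not affected.

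The conclusion rests on two assumptions. The first is that the values posted on the bike follow the Appendix I layout; the text says that calculated values are posted but does not name the form. The second is that the sponsor intends moderate riding throughout, as Table 1 and the risk section indicate. Appendices V and VI could not be checked. If they are clear, riders may be guided correctly, but the Intervention sections and Appendix I would still disagree with Table 1 and the safety instruction.

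**What to change.** 1. In the Study 1 Intervention section and both places in the Study 2 Intervention section, write: *Maximum heart rate = 220 − age. Study target = moderate, 50–70% of maximum; partnered riders follow Table 1.*
2. In Appendix I, print only the moderate range as the study target (70 to 98 beats/min in the age-80 example). Show 98 to 119 beats/min and the 75-minute goal under *General CDC/AHA reference, not the study target*.
3. Check Appendices V and VI, and align them if they carry the 50–85% span.

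If the sponsor does intend vigorous riding outside scheduled sessions, it should say so in place of items 1 and 2, and amend the moderate-only instruction to match.

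The cost is a few sentences, one printout and a check of two sheets. Visits, procedures and data collection do not change. The solo arm's printout would read differently, but only to match the instruction that arm already receives; its self-directed progression stays as it is.
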